WH 3c – We hypothesize that low levels of direct metabolites of EPA, in particular HETEs and the E-series-resolvins (RvE1 & 2) will be a strong predictor of Omega-3 fatty acids response.

WH 4a – Based on the meta-analysis of Lin et al [54], we hypothesize that severity of depressive symptoms will be associated with a pro-inflammatory state, as well as an increase in omega-6/3 ratio and a decrease in omega-3 index. Normalization of these parameters will correlate with improvements in depression scores (CDRS-R, DIKJ).

WH 4b - Based on the study by Huan et al [52], we assume an inverse correlation between Omega-3 fatty acids and suicidal ideation (SIQ-Jr), in particular high levels of EPA will protect against suicidal ideation.

WH 4c – Based on the study by Beier et al [209] we assume that low Omega-3 fatty acids, in particular low EPA levels (and a low omega-3 index) will be associated with affect dysregulation, impulsivity/ emotionality (IES-27) and overall psychopathology.

WH 4d – Based on Kiecolt-Glaser et al [205], we hypothesize that high levels of overall stress (as measured with the PSS scale) will correlate with low levels of Omega-3 fatty acids, a pro-inflammatory state, increased saliva cortisol, and high levels of PUFAs oxidation products as

measured by F2 Isoprostanes in the urine and be inversely correlated with the Conner-Davidsons Resilience Scale.

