- **WH4a:** We will test association between pro-inflammatory state and depressive symptoms by calculating Pearson's correlation coefficient or Spearman's correlation coefficient between the severity of symptoms at baseline and the ratio between pro- and anti-inflammatory markers. The same procedure is also applied to omega-6/3 ratio and omega-3 index. To test whether normalization of these parameters will correlate with improvements in depression scores we'll run a linear regression model with depression scores as dependent, and time and pro-inflammatory state, increase in omega-6/3 and omega-3 index as independent variables.
- **WH4b:** We will calculate Pearson's correlation coefficient or Spearman's correlation coefficient of omega-3 index with SIQ-Jr scores depending on the distribution of the data.
- **WH4c:** As above, we will calculate either Pearson's correlation coefficient or Spearman's correlation coefficient (depending on the distribution of the data) between omega-3 index and scores on the IES-27 and overall psychopathology scores.
- **WH4d:** We also test correlations between levels of Omega-3 fatty acids with salvia cortisol, F2 isoprostanes and Connor-Davidsons Resilience Scale scores by

calculating Pearson's correlation coefficient or Spearman's correlation coefficient, respectively.

- **WH5a:** In order to compare treatment groups regarding occurrence of SUSARs, we will run a two proportions z-Test. Differences in suicidal ideation scores are tested by independent t-Test (for normal distributed data) or Mann-Whitney-U-Test (for non-normal data).

The analyses will be performed after closure of the database. The trial statisticians will perform all a-priori defined statistical analyses according to the statistical analyses plan. All other clinical outcome analyses will be declared as post-hoc analysis.

Future analysis based on the BioBank or other add on projects will be subject of an own protocol with separately formulated hypotheses that will be approved the appropriate authorities.

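### The analysis listed for WH4d leaves out the perceived stress scale, so none of its five hypothesised correlations is computed; in WH4b and WH4c the EPA-specific parts have no test

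*Protocol*

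**What the plan says.** **WH4d, hypothesis (Protocol 5.2).** The sentence is about stress: "we hypothesize that high levels of overall stress (as measured with the PSS scale) will correlate with low levels of Omega-3 fatty acids". It continues with "a pro-inflammatory state, increased saliva cortisol, and high levels of PUFAs oxidation products", the last measured as urinary F2-isoprostanes, and ends with an inverse correlation with the Connor-Davidson Resilience Scale (CD-RISC).

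**WH4d, analysis (Protocol 11.4.3).** "We also test correlations between levels of Omega-3 fatty acids with salvia cortisol, F2 isoprostanes and Connor-Davidsons Resilience Scale scores", by Pearson or Spearman coefficient.

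**WH4b.** Protocol 5.2 assumes an inverse correlation between omega-3 fatty acids and suicidal ideation on the SIQ-Jr, and adds: "in particular high levels of EPA will protect against suicidal ideation". The analysis is a Pearson or "Spearman's correlation coefficient of omega-3 index with SIQ-Jr scores depending on the distribution of the data".

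**WH4c.** Protocol 5.2 expects low omega-3, "in particular low EPA levels (and a low omega-3 index) will be associated with affect dysregulation", impulsivity/emotionality on the IES-27 and overall psychopathology. The analysis correlates the omega-3 index with IES-27 and overall psychopathology scores.

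**The index.** WH3b in Protocol 5.2 says that EPA and DHA are used to calculate it.

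**SAP.** Section 2 of version 1.0 limits the plan to efficacy and safety, and reserves the relationships of inflammatory and lipid markers with symptoms for future analysis plans and manuscripts.

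**The concern.** Protocol 11.4.3 introduces its WH-labelled list as the analyses that test the secondary working hypotheses. For WH4d the variable on which the hypothesis turns has been replaced by another: omega-3 takes the place of PSS. Followed as written, the plan produces a result carrying the WH4d label that says nothing direct about perceived stress, and a reader of the eventual report could take it as evidence for or against a stress hypothesis.

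For WH4b and WH4c the stake is smaller. The protocol attributes clinical efficacy to EPA-rich rather than DHA-rich preparations (3.4.2) and names EPA in both hypotheses, yet no planned correlation for either uses the EPA level.

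The time point also matters. Red-cell fatty acids are measured at screening, week 12 and week 36, and Protocol 8.4 uses them to monitor compliance. Values after randomisation therefore partly reflect the assigned capsule, and a correlation using them without regard to arm would mix treatment allocation with the natural association.

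**Working it through.** The plan states no figure on this point, so the check is a comparison of variable pairs.

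**Step 1. WH4d: hypothesised against planned pairs.**

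| Pair | Hypothesis (5.2) | Analysis (11.4.3) |
|---|---|---|
| PSS with omega-3 | yes | no |
| PSS with pro-inflammatory state | yes | no |
| PSS with saliva cortisol | yes | no |
| PSS with F2-isoprostanes | yes | no |
| PSS with CD-RISC | yes (inverse) | no |
| Omega-3 with saliva cortisol | no | yes |
| Omega-3 with F2-isoprostanes | no | yes |
| Omega-3 with CD-RISC | no | yes |

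Five pairs are hypothesised and three are planned. The overlap is 0 of 5.

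**Step 2. Is PSS used elsewhere?** Protocol 11.4.3 lists PSS-10 among the scales compared between treatment groups, and 11.4 plans baseline to week 36 comparisons for all scales. Neither is a correlation with a marker or with CD-RISC. WH4a uses the inflammatory ratio, but with depressive symptoms. The SAP has no PSS analysis.

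**Step 3. Could the planned pairs stand in?** Let r1 be the PSS/omega-3 correlation and r2 the omega-3/cortisol correlation. The PSS/cortisol correlation must lie within

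r1·r2 ± √[(1 − r1²)(1 − r2²)].

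The plan estimates only r2. With r1 free, the range is −1 to 1: r1 = r2 gives an upper limit of r2² + (1 − r2²) = 1, and r1 = −r2 gives a lower limit of −1. Even if r1 were known, the range would stay wide. The documents give no correlations, so these values are assumptions:

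- r1 = r2 = −0.3: 0.09 ± 0.91, that is −0.82 to 1.00
- r1 = r2 = −0.5: 0.25 ± 0.75, that is −0.50 to 1.00
- r1 = r2 = −0.7: 0.49 ± 0.51, that is −0.02 to 1.00

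The planned pairs do not settle the hypothesised ones.

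**Step 4. WH4b and WH4c.**

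| Part of the hypothesis | Tested? |
|---|---|
| WH4b: omega-3 in general with SIQ-Jr | yes, through the index |
| WH4b: EPA with SIQ-Jr | no |
| WH4c: low omega-3 index with IES-27 and overall psychopathology | yes |
| WH4c: EPA with the same scores | no |

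The same bound shows how loosely the index result constrains EPA. Assume an index/SIQ-Jr correlation of −0.2:

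- EPA/index correlation 0.5: −0.10 ± 0.85, that is −0.95 to 0.75
- EPA/index correlation 0.7: −0.14 ± 0.70, that is −0.84 to 0.56
- EPA/index correlation 0.9: −0.18 ± 0.43, that is −0.61 to 0.25

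Under these assumptions the index result does not fix even the sign for EPA.

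**Step 5. Time point.** The first WH4a correlation names baseline severity. The entries for WH4b, WH4c and WH4d name no visit.

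**The case against.** The strongest reply is about consequence. These are secondary biomarker hypotheses, and Protocol 3.7 calls the link between suicidal ideation or aggression and bioactive lipids a more explorative aim. The current SAP hands the whole area to later plans. Protocol 9.2.2.4 has the prediction markers other than hsCRP measured after the last patient's final visit, apart from baseline data that may be used in add-on projects. A later plan could thus specify the right tests before most marker data exist. This stands, and it limits the weight of the point. It does not remove it: until such a plan is written, 11.4.3 is the only prespecified analysis for WH4d, and a plan drafted from it would carry the mismatch forward.

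Four stronger readings are tempting, and the documents do not support them:

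- *That WH4b and WH4c go untested.* The index tests the general statement in WH4b, and WH4c names the index itself. Only the EPA-specific parts are missing.
- *That the PSS correlations would have to be declared post hoc.* Protocol 11.4.3 and 11.4.6 attach that label to analyses not defined beforehand. The PSS correlations are hypothesised in 5.2, and the deferred plan can specify them in time.
- *That the mismatch can be expressed as a loss of power.* That needs correlations the documents do not give, and a number of complete samples that is unknown, since 9.2.2.4 lets participants decline later blood, urine or saliva sampling. The fault is the wrong pair of variables, not too few patients.
- *That visits will be pooled after randomisation.* The plan does not say so; it leaves the visit open.

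It is also fair to say that using pre-treatment values is a choice. WH4b speaks of protection, and the objectives include illness course, so later visits may be of interest too.

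**Conclusion.** The WH4d mismatch holds in full: 0 of 5 hypothesised correlations is planned, the inflammatory markers are missing as well as PSS, and nothing elsewhere in the protocol or SAP repairs it. This is a count from the text and rests on no numerical assumption. The ranges in the working are illustrations under assumed correlations.

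The WH4b and WH4c point holds in a milder form: both hypotheses are partly tested, and the gap is the EPA-specific part of each. The missing time point for WH4b to WH4d is an omission to close, not evidence that a biased analysis is planned.

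The primary endpoint, the safety analyses, the sample size and everything in SAP version 1.0 are unaffected. The correction is worth making because it is specific and nearly free.

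**What to change.** In Protocol 11.4.3, or in the follow-up biomarker analysis plan before the markers are analysed:

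- **WH4d:** correlate baseline PSS-10 with omega-3 levels, the pro-/anti-inflammatory ratio, saliva cortisol, urinary F2-isoprostanes and CD-RISC. If the three omega-3 pairs now listed are kept, report them as what they are and not as the test of WH4d.
- **WH4b:** keep the omega-3 index with SIQ-Jr, and add red-cell EPA with SIQ-Jr.
- **WH4c:** keep the omega-3 index with IES-27 and overall psychopathology, and add red-cell EPA with both.
- **Time point:** state that these cross-sectional correlations use pre-treatment values, and adjust any analysis of later visits for treatment arm.

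The cost is a few more secondary correlations: 5 for WH4d, 1 for WH4b and 2 for WH4c, so 5 + 1 + 2 = 8 if each measure contributes one score. No new data are needed. PSS-10, CD-RISC, SIQ-Jr and IES-27 are scheduled at baseline, and blood, urine and saliva at screening (Protocol 9.1).

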11.4.4 Interim Analyses

No interim analyses are carried out to maintain the blinding of all researchers over the whole course of the study. Only the IDMC will run an interim analysis after 60 patients to ensure the safety of the patients as specified in the IDMC SOP. If the IDMC considers the number of study participants insufficient to address the primary outcome in the due course of the study (e.g. because of too many drop outs, not sufficient prepubertal participants, other reasons...), the total sample size may be reconsidered.

11.4.5 Safety Analysis

Safety and harms frequency data will be described based on actual treatment received using MedDRA (integrated in SecuTrial®) and the self-report side effect checklist (ASEC). The rate of harm- and suicide-related adverse events (e.g. SIQ-Jr) in each treatment group will be compared using χ^2 and Fisher exact tests, and ORs will be calculated to provide an indicator of relative risk of the active versus the placebo condition.

11.4.6 Deviation(s) from the Original Statistical Plan

We will report protocol violations (non-adherence to the treatment protocol) in the CONSORT flow chart, in the methodology section and if appropriate in the discussion. We will state how many participants will have been included in the placebo-lead in phase, how many of those dropped below a CDRS-R score of 40 within the lead in phase, how many will have been randomized, how many dropped out within the first six weeks due to non-compliance and how many will have completed the acute and maintenance treatment phase. The intention-to-treat (ITT) approach includes all randomized patients. We will declare all analysis not defined a priori as post hoc analysis.

11.5 Handling of Missing Data and Drop-Outs

As stated above, the random coefficient regression models explained above already deal with missing data. For all other analysis we will use multiple imputations for missing data as described by Rubin [255, 256].

12 ELIGIBILITY OF THE PROJECT SITE(S)

The department of Child and Adolescent Psychiatry of the University of Zurich is the biggest institution of its kind in Switzerland with close to 400 employees and is well suited to accommodate a clinical study. All the project sites are well-established official treatment centres for pMDD, and emergency care is readily available at each institution. All the centres are in close proximity to the lead centre, and many of the senior clinicians were trained or worked as consultants in the academic lead centre (ZH). Furthermore, the academic and non-academic centres have a joint training program for their trainees for several years providing a good foundation for similar concomitant treatment of pMDD.

13 DATA QUALITY ASSURANCE AND CONTROL

The Sponsor-Investigator is implementing and maintaining quality assurance and quality control systems with written SOPs and Working Instructions to ensure that trials are conducted and data are generated, documented (record), and reported in compliance with the protocol, GCP, and applicable regulatory requirement(s).

The Sponsor-Investigator is responsible to have written SOP's and WIs in place for the study and to provide those to all participating study sites. The Principal Investigators at all sites must have a manual of the relevant SOPs and WIs for the study on site and are responsible for proper training of all involved study personnel for the respective procedures.

Monitoring and Audits will be conducted during the course of the study for quality assurance purposes.

13.1 Data Handling and Record Keeping / Archiving

The study will strictly follow the protocol. If any changes become necessary, they must be laid down in an amendment to the protocol. All amendments of the protocol must be signed by the Sponsor-Investigator and submitted to CEC and Swissmedic.

13.1.1 Case Report Forms

The investigators will use electronic case report forms (eCRF), one for each enrolled study participant, to be filled in with all relevant data pertaining to the participant during the study. All

participants who either entered the study or were considered not-eligible or were eligible but not enrolled into the study additionally have to be documented on a screening log. The investigator will document the participation of each study participant on the Enrolment Log.

For data and query management, monitoring, reporting and coding an internet-based secure data base secuTrial® developed in agreement to the Good Clinical Practice (GCP) guidelines provided by the Clinical Trials Center (CTC) Zurich will be used for this study. It is the responsibility of the investigator to assure that all data in the course of the study will be entered completely and correctly in the respective data base. Corrections in the eCRF may only be done by the investigator or by other authorised persons. In case of corrections the original data entries will be archived in the system and can be made visible. For all data entries and corrections date, time of day and person who is performing the entries will be generated automatically.

ECRFs must be kept current to reflect participant status at each phase during the course of study. Participants must not to be identified in the eCRF by name. Appropriate coded identification (e.g. Participant Number) must be used.

It must be assured that any authorised person, who may perform data entries and changes in the eCRF, can be identified. A list with signatures and initials of all authorised persons will be filed in the study site file and the trial master file, respectively.

Documented medical histories and narrative statements relative to the participant's progress during the study will be maintained. These records will also include the following: originals or copies of laboratory and other medical test results which must be kept on file with the individual participants' eCRF. A detailed listing of all the study parameters for each participant can be found in the Study Manual.

The investigators assure to perform a complete and accurate documentation of the participant data in the eCRF. All data entered into the eCRF with exception of self-rating instruments that are entered directly online by the study participant/ parents and computerized neurocognitive data (for which data the eCRF will be source data) will also be available in the individual participant file either as print-outs or as notes taken by either the investigator or another responsible person assigned by the investigator.

Essential documents must be retained for at least 10 years after the regular end or a premature termination of the respective study (KlinV Art. 45). Any patient files and source data must be archived for the longest possible period of time according to the feasibility of the investigational site, e.g. hospital, institution or private practice.

13.1.2 Specification of Source Documents

The following documents are considered source data, including but not limited to:

- SAE worksheets
- Nurse records, records of clinical coordinators, and
- Medical records from other department(s), or other hospital(s), or discharge letters and correspondence with other departments/hospitals, if participant visited any during the study period and the post study period.

Source data must be available at the site to document the existence of the study participants and substantiate the integrity of study data collected. Source data must include the original documents relating to the study, as well as the medical treatment and medical history of the participant.

The following information (at least but not limited to) should be included in the source documents:

- Demographic data (age, sex)
- Inclusion and Exclusion Criteria details
- Participation in study and signed and dated Informed Consent Forms
- Visit dates
- Medical history and physical examination details (including documentation of scars)
- Key efficacy and safety data (as specified in the protocol)
- AEs and concomitant medication
- Results of relevant examinations
- Laboratory printouts
- Dispensing and return of study drug details
- Reason for premature discontinuation
- Randomization number

13.1.3 Record Keeping / Archiving

In accordance with Swiss national laws and guidelines and the specifications of the ICH-GCP guidelines, the investigators from participating sites and the coordinating centre are obligated to archive all documents pertaining to the study for 10 years after the last subject has completed or discontinued from the study. Electronic data will be archived at the CTC on a server pertaining to the University hospital of Zurich.

13.2 Data Management

Research assistants and local investigators will enter the acquired data and examination results into an eCRF (SecuTrail®) that is accessible via the internet. Investigators will receive personal user names and passwords for this purpose, and data will be encrypted for transfer. For each site, it will be agreed before the start of the study which documents serve as source documents for all data entered into the eCRF. The investigator must (electronically) sign that entries into the eCRF are true and complete. At least a subset of data will be entered doubly to ensure data quality.

Study sites and associated investigators will be carefully selected and comprehensively informed and trained regarding GCP, all study procedures and the required examinations and documentation before the start of the study. The quality of data acquisition will be ensured by regular monitoring visits and the continuous availability of the monitor and trial-coordinator for consultation. After data have been submitted to the study centre, another thorough inspection of the completeness and plausibility of entries will be conducted. If needed, questions for clarification will be addressed to the sites. Only after all questions regarding data quality have been answered, the database will be locked.

13.2.1 Data Management System

For the electronic data capture, storage, monitor and export for statistical analyses, the latest version of the study software SecuTrial® will be used. SecuTrial® meets the regulatory requirements according to GCP and FDA 21 CFR Part 11. SecuTrial® is installed on a secure server provided by the University Hospital of Zurich. Only members of the CTC can access the server. The sponsor will set up the software before starting the trial under close supervision of the data manager of the CTC. All users will be trained in the handling of the software and SOPs will be available at each site file and in the master trial file.

13.2.2 Data Security, Access and Back-up

The sponsor is responsible for granting access to the electronic data. Every involved party will get his own password protected login and associated authorization. An audit trail documents all changes that are made in the system. All communication between the software and its users will be encrypted and a firewall protects the access to the software. A backup of the data will be made every 24 hours, and the University Hospital of Zurich provides a backup server in case the main server would be compromised.

13.2.3 Analysis and Archiving

After data validation the sponsor will notify the CTC about the closure of the database. After that, no new data or changes to existing data can be made. However, the data can still be accessed and be used for statistical analyses. After the last statistical analyses have been completed, the sponsor will notify the data manager about the timing of the archiving of the database, after which the project cannot be accessed anymore. After archiving, the database can only be accessed by written request of the sponsor or on request of the relevant authorities.

